#### 11.3.2.3 Summary Statistics

For each laboratory variable, summary statistics (see Section [1.3.1](#)) by treatment group will be provided for test results and their change from baseline-ENR (quantitative variables only) at each visit up to and including the End-of-Trial Visit for the Safety-ENR analysis set; and for test results and their change from baseline-RT (quantitative variables only) at each visit up to and including the End-of-Trial Visit for the Safety-RT Analysis Set. The number and percent of subjects with clinically significant laboratory abnormalities according to the investigator’s assessment of the categories ‘normal’, ‘abnormal, not clinically significant’, and ‘abnormal, clinically significant’ will be presented. For Visits 2, 3, and 4, the Safety-ENR analysis set will be used; for post-randomization visits, the Safety-RT analysis set will be used.

#### **11.3.2.4 Laboratory Variable Changes Relative to Normal Range**

Shift tables will be presented on an as-needed basis only.

#### **11.3.3 Vital Signs**

##### **11.3.3.1 Visits and Visit Windows**

- Baseline for all vital signs analyses will be the values obtained at the last assessment before the subject received the first dose of the IMP during the enrichment period.
- Treatment-emergent vital signs data will be defined as specified for AEs in Section [11.3.1.1](#).
- End of trial will include the last post-baseline observation during the trial.
- Data will be analysed by planned visit using the visit-window structure as described in Section [3.1.5](#).

##### **11.3.3.2 Summary Statistics**

For each vital sign variable, summary statistics (see Section [1.3.1](#)) will be presented for observed values as well as the investigator's assessment of the categories 'normal', 'abnormal, not clinically significant' and 'abnormal, clinically significant'. For Visits 2, 3, and 4, the Safety-ENR analysis set will be used; for post-randomization visits, the Safety-RT analysis set will be used.

#### **11.3.4 ECGs**

- ECG will be categorized as 'normal', 'abnormal, not clinically significant', and 'abnormal, clinically significant'.
- Baseline for ECG is the assessment at the Screening Visit.
- Randomized-treatment-emergent ECG is the ECG at the End-of-Trial Visit.

The ECG variable will be summarized overall for the Safety-ENR analysis set and by treatment for the Safety-RT analysis set. Shift tables will be presented on an as-needed basis only.

#### **11.3.5 Other Safety Variables**

##### **11.3.5.1 Weight Changes**

- Weight Change will be derived as weight at the current visit minus weight at the previous visit using the visit-window structure described in Section [3.1.5](#).
- Data will be analysed by planned visit using the visit-window structure as described in Section [3.1.5](#).
- Enrichment-treatment-emergent weight changes comprise weight changes from Visit 2 to Visit 3 and weight changes from Visit 3 to Visit 4. Post-randomization weight changes are considered randomized-treatment-emergent weight changes
- The end of trial value for a subject will include the last post-baseline-ENR observation for the subject during the trial.

Summary tables will be presented by visit displaying the number and percentage of subjects with a weight change of more than 2 kg since the previous visit.

#### **11.3.5.2 Physical examination**

- Physical examination findings will be categorized according to 'normal', 'abnormal, not clinically significant', and 'abnormal, clinically significant'.
- Baseline-ENR for the physical examination is the assessment at the Screening Visit, baseline-RT is the assessment at Visit 4, and End of Trial will include the last post-baseline-RT assessment during the trial.

Summary tables will be prepared by visit for the Safety-ENR analysis set, and by visit and treatment for the Safety-RT analysis set. Shift tables will be presented on an as-needed basis only.

## 12 Interim analyses

The safety data will be reviewed on a regular basis by a Data Monitoring Committee (DMC) as described in a separate DMC charter.

After 125 subjects have been randomized and every 8 weeks thereafter, an interim analysis is performed by [REDACTED]. Each of these interim analyses comprises a futility analysis and, until end of recruitment, an update of allocation probabilities for the FE 201836 doses based on a Bayesian analysis of the dose-response relation. The updating of the allocation probabilities is focused on improving the design with regard to the identification of the MED and the ED85.

In contrast to the primary analysis, the interim analyses will not be adjusted for baseline number of nocturnal voids.

In the first interim, the futility stopping rule is to stop for futility if  $\Pr(\mu_{500} - \mu_{Plb} < -0.3) < 10\%$ . In the later interim analyses, the futility rule is to stop for futility if  $\Pr(\mu_{500} - \mu_{Plb} < -0.3) < 5\%$ . At all these trial updates, Bayesian estimates will be used to update the allocation probabilities for the doses of FE 201836. The allocation probability for each dose  $d$  of FE 201836 is proportional to the posterior variance of  $\mu_d$  multiplied by the average of  $\Pr(d \text{ is the MED})$  and  $\Pr(d \text{ is the ED}_{85})$ , and divided by  $n_d + 1$ .

The power and the probability of making a false positive conclusion using the adaptive design was investigated based on simulations as described in the trial protocol.

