Treatment	Investigational Medicinal Product	
	Active Substance	Placebo
Active Run-in		
500 µg FE 201836	500 µg FE 201836 oral solution	Placebo ODT
Washout		
-	-	-
Randomised Trial Period		
Up to First Interim Analysis		
500 µg FE 201836	500 µg FE 201836 oral solution	Placebo ODT
Desmopressin	Desmopressin ODT (25µg for females and 50 µg for males)	Placebo oral solution
Placebo	-	Placebo oral solution and Placebo ODT
After First Interim Analysis		
50 µg FE 201836	50 µg FE 201836 oral solution	Placebo ODT
100 µg FE 201836	100 µg FE 201836 oral solution	Placebo ODT
150 µg FE 201836	150 µg FE 201836 oral solution	Placebo ODT
250 µg FE 201836	250 µg FE 201836 oral solution	Placebo ODT
350 µg FE 201836	350 µg FE 201836 oral solution	Placebo ODT
500 µg FE 201836	500 µg FE 201836 oral solution	Placebo ODT
Desmopressin	Desmopressin ODT (25µg for females and 50 µg for males)	Placebo oral solution
Placebo	-	Placebo oral solution and Placebo ODT

DURATION OF TREATMENT

The duration of the trial is approximately 16 weeks. Subjects will be screened, enter a 2-week lifestyle changes period followed by a 1-week single-blind active run-in and 1-week washout prior to randomisation. Following randomisation, the first 125 subjects will be treated daily with placebo, 500 µg FE 201836 or desmopressin (25 µg for females and 50 µg for males) for up to 12 weeks. When the first 125 subjects have been randomised an interim analysis will be conducted and a decision taken on whether to continue the trial as planned or stop the trial for futility.

If the decision is to continue the trial as planned, subjects may be randomised to one of 8 treatment groups for 12 weeks: placebo, 50 µg FE 201836, 100 µg FE 201836, 150 µg FE 201836, 250 µg FE 201836, 350 µg FE 201836, 500 µg FE 201836, or desmopressin (25 µg for females and 50 µg for males).

STATISTICAL METHODS

Primary Analysis Model used in the Response-adaptive Trial Design

The primary analysis is based on a time-course hierarchical longitudinal model, i.e.,

$$Y_{t,i} = e^{\gamma t}(\mu_{d,i} + \delta_i) + \varepsilon_t$$

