where $Y_{t,i}$ is the change from baseline in number of nocturnal voids at visit t for subject i , d is the dose, $e^{\gamma t}$ the fraction of the effect at Visit t (Week 1, Week 4 or Week 8) as compared to the Month 3 visit ($\gamma_t=0$ at Month 3), δ_i the random subject effect and ε_t the independent $N(0, \lambda_t^2)$ distributed error term. The dose-response for subject i , $\mu_{d,i}$, is adjusted for the number of baseline voids ($x_{0,i}$) and modelled using the sigmoidal E-max model, i.e.,

$$\mu_{d,i} = \beta x_{0,i} + \alpha_1 + \frac{(\alpha_2 - \alpha_1) d^{\alpha_4}}{d^{\alpha_4} + \alpha_3^{\alpha_4}} = \beta x_{0,i} + \mu_d$$

Inference will be based on a Bayesian analysis using sufficiently non-informative priors on respective parameters. The trial will be considered successful if the maximum dose has a greater than 97.5% posterior probability of being better than placebo, i.e., if $\Pr(\mu_{\text{MAX}} < \mu_{\text{Plb}}) > 97.5\%$.

Response-adaptive Decision Rules

The double-blind treatment period is based on a response-adaptive Bayesian top-down design. After an initial 125 subjects have been randomised to placebo, 500 µg FE 201836 (the highest dose) or desmopressin in a 2:2:1 ratio an interim analysis will take place to stop for futility if the $\Pr(\mu_{\text{MAX}} - \mu_{\text{Plb}} < -0.3) < 10\%$, where $\Pr(\cdot)$ denotes posterior probability (under the assumed monotonic dose-response relation, i.e. smaller doses will be less effective).

If not stopped for futility, all treatment arms will be opened up for randomisation, subjects can be randomised to placebo, desmopressin or to any FE 201836 dose (50-500 µg) in a 2:1:7 ratio. When allocated to a FE 201836 dose (7/10), unrestricted randomisation will be used to allocate a subject

to a specific FE 201836 dose using an allocation probability that is the average of $I(\text{dose is MED})$ and $I(\text{dose is ED}_{85})$, where $I(\text{target})$ is the probability that “dose is target” scaled by the squared standard error at that dose. The MED is the lowest dose that has at least a $\Delta=0.3$ larger reduction in mean nocturnal voids as compared to placebo and the ED_{85} is the lowest dose that achieves at least 85% of the effect of the maximum dose (500 μg).

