9.7.2 Primary Analysis

The objectives of the primary analysis are to establish Proof-of-Concept of FE 201836 and to estimate the dose-response profile of FE 201836. The dose-response is the average reduction from baseline in nocturnal voids during the randomised period. Proof-of-concept will be evaluated by the posterior probability that FE 201836 has superior efficacy as compared to placebo. Similarly, interim analysis futility criteria will be evaluated by pre-defined quantities of interest.

This section provides a brief background on the statistical Bayesian model that is utilised.

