2.1 Adjustments in Primary Analysis

The primary analysis applied to actual trial data will be adjusted for the number of baseline voids x_0 . This implies that the actual fitted dose-response model for subject i will be

$$\mu_{d,i} = \beta x_{0,i} + \alpha_1 + \frac{(\alpha_2 - \alpha_1) v_d^{\alpha_3}}{v_d^{\alpha_3} + \alpha_3^{\alpha_3}}$$

The prior distribution for β is modelled as

$$\beta \sim N(0, 10^2)$$

For the purposes of evaluation of trial design and operating characteristics, the model without the adjustment for number of baseline voids will be fitted to simulated trial data.

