2.3 Evaluation of Posterior Estimates

The Bayesian model fitted to the data at each update contains a final endpoint dose-response model and a longitudinal model used for imputing the final mean change from baseline. The posterior distribution for the dose-response parameters is calculated as follows.

1. A longitudinal model is created to link all the visit integrated mean changes from baseline observations to the final integrated mean change over the visits. We label the model as

$$g(y_{it}|\gamma, \delta, \mu, \lambda) \sim e^{\gamma t}(\mu_d + \delta_i) + N(0, \lambda_f^2) \quad t=1,2,3,4$$

2. We created a dose-response model for the inference of the dose-response parameters given the final visit mean integrated change from baseline, y_i (the mean change from baseline of the four visits, which is y_{i4})

$$f(y_i|\alpha, \sigma) \sim \alpha_1 + \frac{(\alpha_2 - \alpha_1)v_{d_1}^{\alpha_4}}{v_{d_1}^{\alpha_4} + \alpha_3} + N(0, \sigma^2) \quad i=1, \dots, n$$

The posterior distribution of the dose-response parameters is calculated using Markov chain Monte Carlo simulation. In the algorithm the following steps are taken

- A. An observation of the parameters of the longitudinal model ($\gamma, \delta, \mu, \lambda$) are drawn from their complete conditionals.
- B. An observation for the final mean integrated change from baseline for each subject with incomplete data is imputed from $g(y_{it}|\gamma, \delta, \mu, \lambda)$ conditional on the draws from A.
- C. An observation from the complete conditional distribution of the parameters

Trial Code: 000233

of the dose-response model (α, σ) is drawn given the complete data imputed in B and the naturally completed data in the trial.

- D. Any posterior distribution summaries are tabulated from the draws in C that are past the burn-in period of the MCMC algorithm.
- E. Repeat A-D for the length of the chain.

Individual parameters are updated by Metropolis Hastings (or Gibbs sampling where possible), using only the y_i and y_{it} data available at the time of the update.

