**Table 1 Posterior Probabilities of Interest**

Quantity of Interest	Posterior Probability within the Trial that:	Objective
$Pr(\mu_{500} < \mu_{Plb})$	the effect of 500 µg FE 201836 during the 12 weeks of randomized treatment is superior to placebo	Proof-of-Concept
$Pr(\Delta_{500} < -0.3)$	500 µg FE 201836 has more than 0.3 voids reduction in nocturnal voids as compared to placebo	Futility
$Pr(\text{dose } d \text{ is MED})$	dose $d$ is the MED	Establish the MED
$Pr(\text{dose } d \text{ is } ED_{85})$	dose $d$ is the $ED_{85}$	Establish $ED_{85}$

In the trial updates of the allocation probabilities, the two posterior probabilities:  $\Pr(\text{dose } d \text{ is MED})$  and  $\Pr(\text{dose } d \text{ is ED}_{85})$ , are used in the updated allocation probability for dose  $d$ . The trial updates are performed as analyses without baseline adjustment, thus, they are not based on the model used for the primary analysis in the reporting of the trial. For additional information, see Section 12.

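### Interim futility and dose allocation omit the baseline adjustment used in the protocol's model and the final analysis, leaving avoidable noise that SAP Section 14 does not explain

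*SAP*

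**What the plan says.** **SAP.** Section 12 makes each interim a futility check plus, while recruitment lasts, an update of the allocation probabilities, and then says: "In contrast to the primary analysis, the interim analyses will not be adjusted for baseline number of nocturnal voids". Section 3.1.1, in the text after Table 1, says of the updates: "The trial updates are performed as analyses without baseline adjustment, thus, they are not based on the model used for the primary analysis". Section 3.1.3 repeats that allocation uses the unadjusted curve. The final model in Section 10.2.1 carries a term beta(x0 - 2), both in the endpoint model and in the longitudinal imputation model.

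**Protocol body.** The synopsis heads its model "Primary Analysis Model used in the Response-adaptive Trial Design", and the dose-response in that model "is adjusted for the number of baseline voids". Section 9.7.2.1 sets out the same adjusted model. Its Table 9-2 lists the futility, MED and ED85 quantities as outputs of that model, and the last two also set the allocation weights. Section 9.11.2 refers back to Table 9-2 for the interim futility rule.

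**Protocol Appendix 2.** The section on adjustments says "The primary analysis applied to actual trial data will be adjusted for the number of baseline voids". For evaluating the design, it says "the model without the adjustment for number of baseline voids will be fitted to simulated trial data". Section 2.3 opens with "The Bayesian model fitted to the data at each update contains a final endpoint dose-response model and a longitudinal model", and the formulas beneath it have no baseline term.

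**SAP Section 14.** This lists one change to the interim analyses, the factor 1/(n_d + 1) in the allocation weights. It does not list the missing adjustment.

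**The concern.** The endpoint is a change from baseline, so the baseline count is already in hand for every subject who contributes to an interim, and using it as a covariate costs no subjects. If change depends on baseline, an unadjusted contrast carries variance that the final model would remove. That noise enters two decisions that cannot be revisited: whether to stop, and which doses receive the stage 2 subjects. The first interim is the most exposed, because it rests on 50 placebo subjects against 50 on 500 µg.

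A second route opens later. Doses below 500 µg are randomised only in stage 2, while placebo pools both stages. A change in mean baseline voids between stages would then enter the unadjusted low-dose contrasts.

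**Working it through.** **1. The plan's own figure.** Inputs: SD 0.95 (Protocol 9.1; Appendix 2, 4.1.1), 50 v 50 (Appendix 2, 3.1), and stopping if Pr(difference < -0.3) < 10% (Protocol Table 9-3). With a flat prior and complete data:

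- SE = 0.95 × sqrt(2/50) = 0.190
- Stop if the observed difference exceeds -0.3 + 1.2816 × 0.190 = -0.056
- P(stop | null) = Phi(0.3/0.190 - 1.2816) = Phi(0.297) = 61.7%

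Table 9-1 states 75.8%, so the figure is not reproduced. A simulation of the whole design used Appendix 2's priors, accrual, dropout and longitudinal fractions, with the variance treated as known and the SAP's allocation rule. It gives about 58% for null first-interim stopping, power of 93.1% against the stated 90.4% in Scenario III, and null success of 2.1% against 3.0%. It only approximates the sponsor's simulator and is not evidence that the table is wrong. If 75.8% of null trials ended at 125 subjects and the rest ran to 300, the average would be 0.758 × 125 + 0.242 × 300 = 167, below the stated 200. The first-interim column may therefore count cumulative early futility. Only differences between unadjusted and adjusted interims are used below.

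**2. Precision at the first interim.** Let rho be the correlation between baseline voids and the average change. It is not in the documents; 0.3 to 0.5 is assumed, and 0.95 is taken as the unadjusted SD. Adjusted SE = 0.190 × sqrt(1 - rho²).

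| rho | SE | Relative information | P(stop), null | P(stop), Scenario III |
|---|---|---|---|---|
| 0 | 0.190 | 1.00 | 61.7% | 1.2% |
| 0.3 | 0.181 | 1.10 | 64.6% | 1.0% |
| 0.5 | 0.165 | 1.33 | 70.6% | 0.8% |

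Variance falls by rho², that is 9% to 25%. Null stopping rises by 2.9 to 8.9 points.

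**3. Whole design.** 1,000 simulated trials per cell, final analysis adjusted throughout, unadjusted interims → adjusted interims:

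| rho | Scenario | First-interim stop | All early stops | Final success |
|---|---|---|---|---|
| 0.3 | Null | 58.2 → 61.0% | 79.7 → 82.1% | 1.4 → 2.1% |
| 0.5 | Null | 58.5 → 67.2% | 80.2 → 88.5% | 1.7 → 1.7% |
| 0.3 | III | 1.4 → 0.7% | 1.4 → 0.7% | 95.5 → 96.3% |
| 0.3 | IV | 1.8 → 1.0% | 2.2 → 1.3% | 91.2 → 90.5% |
| 0.5 | III | 1.7 → 0.7% | 1.7 → 0.7% | 97.0 → 97.9% |
| 0.5 | IV | 2.6 → 0.7% | 3.0 → 0.9% | 94.6 → 95.8% |

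At rho 0.5 the null average sample falls from 186 to 171. The simulation standard error is about 1.6 points for a proportion near 58% (sqrt(0.582 × 0.418/1000)) and about 0.7 points near 95%. Changes in final success of about 1 point, including the one fall, are therefore close to simulation noise.

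**4. Drift between stages.** At full enrolment placebo has 50 + 0.2 × 175 = 85 subjects, of whom 35 are from stage 2. If mean baseline rises by D between stages and change has slope beta on baseline, the raw contrast of a low dose with placebo shifts by beta × D × (1 - 35/85) = 0.59 × beta × D. For assumed beta of -0.3 to -0.5 and D of 0.2 to 0.4 voids this is -0.04 to -0.12 void, against the MED margin of 0.3. In simulation (rho 0.3, Scenario III, 600 trials), a stage 2 shift in the outcome of -0.1 or +0.1 void, carried by baseline, puts 56.8 or 41.9 subjects on 50 to 150 µg with unadjusted interims. With adjusted interims the figure is 48.3 in both cases.

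**The case against.** **The protocol is not of one mind.** A reader might infer that Appendix 2 drops the term for simulated data only and that the SAP plainly overrides it. The text does not go that far. The adjustment paragraph speaks of the primary analysis, and the update formulas in Appendix 2 Section 2.3 have no baseline term, so unadjusted updates followed by an adjusted final analysis is a fair reading. The sentence in Protocol 9.7.2, "Similarly, interim analysis futility criteria will be evaluated by pre-defined quantities of interest", is silent on covariates. The SAP is also open about its choice in three places. All of this stands. What remains is a conflict with the synopsis and Section 9.7.2.1, and no reason given in Section 14.

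**The simulated design was unadjusted.** Unadjusted interims match the model that was evaluated, so the stated operating characteristics already contain this noise. A reader might infer that they are overstated; they are not overstated by this choice. However, the combination now planned, unadjusted interims with an adjusted final analysis, was not simulated either.

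**The drift is speculative.** This largely stands. The re-screening reasons in Protocol 4.2.1 concern voided volume, the NI Diary score, laboratory limits, three exclusion criteria and device faults. None loosens the requirement of at least 2 voids. The SAP rests on protocol version 5.0 and was due before the first interim; on that timetable the loosening fell within stage 1, which dilutes any contrast between stages. The sigmoid shared by all doses also means that the raw-mean shift in step 4 is not the shift in the fitted curve.

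**The final analysis is adjusted.** This stands too. Proof-of-concept and the reported dose-response are estimated with the covariate, so only the interim decisions are exposed.

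**Conclusion.** The point holds as a cheap improvement together with a reconciliation of the documents. The interims leave out a covariate that is free, that the protocol's main text includes and that the final analysis uses, and no reason is given.

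For an assumed rho of 0.3 to 0.5, adjustment would lower interim variance by 9% to 25% and raise correct first-interim stopping of an inactive drug by about 3 to 9 points. Wrongful early stopping in Scenarios III and IV, already 3.0% or less, falls somewhat, and final success moves by about 1 point. These sizes depend on rho, which the documents do not give, and on an approximate simulation that did not reproduce the stated table.

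A reader might infer that baseline drift could cause the first futility stop. It cannot bias that decision, because placebo and 500 µg are randomised concurrently; only chance imbalance matters there. From the second interim on, drift could move low-dose allocation, but its size is undocumented, and adjustment removes only the part carried by baseline voids.

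**What to change.** - In SAP 3.1.1, 3.1.3 and 12, fit the baseline-adjusted model of Section 10.2.1 at every interim, for futility and for allocation, with the beta(x0 - 2) term in the longitudinal part as well.
- If the interim software takes no covariate, pre-adjust the outcomes with visit-specific slopes, estimated with treatment arm in the model and without desmopressin subjects. One constant slope will not do: the longitudinal model scales the baseline term by visit, so at the assumed Week 1 fraction a constant would over-correct by 1/0.8142 - 1 = 23%. A slope pooled over arms without arm terms could be confounded with dose.
- Reconcile the update formulas in Appendix 2 Section 2.3 with the synopsis and Section 9.7.2.1.
- If unadjusted interims are kept, list the departure in SAP Section 14 with a reason, and simulate unadjusted interims with an adjusted final analysis.

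**Cost.** A model term already specified for the final analysis, or a preprocessing step, plus a short text change. The existing operating characteristics would only approximate the adjusted interim rule, so a short re-simulation is advisable; it needs an assumed correlation between baseline and change.
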